### **Figure 1. Flowchart of Study Procedures**

### **Management of Medical Gases Used in Study**

As the research pharmacy does not procure nor dispense gaseous inhalants, medical gases used in the study will be managed per protocol and as per BIDMC's Compressed Gas Cylinder Storage and Handling Policy #: EC-62. Nitrous and oxygen cylinders will be procured through the OR materials management specialist. The tanks for study gases will be stored in an approved gas cylinder storage rack in (Room 385) of the Shapiro Clinic for immediate usage. There is also a gas tank

storage area in the Shapiro OR (close to the clinic) for additional storage. Both spaces are secured and locked off hours. Research staff will only access these supplies as necessary for the study.

## B. Statistical Considerations

### Sample Size Justification

Based on a previous study by Bringman *et al*, the mean (SD) of STAI anxiety score is 34(8). A clinically meaningful decrease, as determined by the Cochrane review group was 0.5 of SD.

Our sample size calculation to detect a 4-point change in pain score (p less than 0.05 significance level) was 64 patients per group ( $\alpha=0.05$ , power=80%). We will inflate our sample size by 15% to account for any missing data or any withdrawal from the study; therefore, our estimated sample size will be 76 patients per group.

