#### Specific Aims:

**Aim 1:** To determine the effectiveness of Self-Administered Nitrous Oxide (SANO) in decreasing patient perceived anxiety and pain related to prostate needle biopsy.

*Hypothesis 1.1: Patients receiving periprocedural SANO will have decreased anxiety during the procedure, as measured by STAI (State-Trait Anxiety Inventory) score, situational pain catastrophizing scale (SPCS) and patient vital signs.*

*Hypothesis 1.2: Patients receiving periprocedural SANO may have a decrease in pain as measured by VAS (visual analogue scale) score and patient vital signs.*

**Aim 2:** To demonstrate that the SANO at the time of prostate biopsy does not significantly increase burden on Urologist productivity, nor increase the difficulty of performing the biopsy.

*Hypothesis 1.1: Administration of periprocedural SANO will not significantly lengthen the time of the procedure relative to local anesthetic alone.*

*Hypothesis 1.2: Administration of periprocedural SANO will result in minimal side effects for the patients and will allow the patient to drive home independently.*

*Hypothesis 1.3: Administration of periprocedural SANO will allow the operating Urologist to perform the procedure with the same ease as on those patients who do not have SANO.*

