### **Pre-procedure Evaluation**

On the day of the biopsy, current standard procedure is to bring the patient to an exam room (separate from the biopsy room) where pre-procedure vitals are obtained. At this time, the pre-procedure STAI and VAS scores will be obtained. Information of inhaled gas administration and how to self-administer will be explained to the patient using templated verbal instructions. It will be emphasized that if at any point during the procedure, the patient feels uncomfortable with the inhaled gas, the team will help remove the mask.

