### Data Analysis

All data will be collected and stored securely using the REDCap system. Data will be managed and analyzed by the PI and biostatistical support team at the BIDMC FIRST program. A Data Transfer Agreement will be created to allow for the study team's statistician, [name] MD/PhD at Brigham and Women's Hospital, to obtain and perform statistical analysis on de-identified data. At the conclusion of the study, de-identified study data will be exported out of REDCap and sent to [name] in a secure file via email message. Data will not be transferred until this agreement is approved and fully executed by both parties.

Primary outcome measure is patient anxiety and pain levels in the N2O group vs the oxygen only group as measured by the VAS and VAS A scores. We are specifically interested in the difference in scores between the two groups. Prostate biopsy mean VAS score with local anesthetic is around 3-4. We will also obtain a baseline pain index between the two groups. We will compare the perioperative VAS and VAS-A scores to the retrospective VAS and VAS-A scores collected during the survey administered 2-10 months after their biopsy.

We will also be obtaining 6 question Situational Pain Catastrophizing Scores for both groups and will compare the variation in response. Patients who have had a prior biopsy will also fill out a 13 question Pain catastrophizing score, which we will use as a baseline measure for biopsy related anxiety and hesitation.

Additional metric will include duration of biopsy, as measured by time in/time out of the procedure room for patients administered either nitrous or control oxygen when compared to patients who do not consent to the study (and will have no gas applied). Operator ease in performing the biopsy will be measured by 3 simple questions assessing patient positioning and ease of transrectal probe insertion. Prostate biopsies are generally performed as an outpatient procedure and patients can drive themselves home in most situations. Post biopsy side effects and ability of the patient to drive themselves home will be used as a surrogate to determine practicality of administering SANO in the outpatient setting.

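### The sample size is an STAI anxiety calculation labelled as pain, while the declared primary outcome is VAS and VAS-A with no SD, target difference or success rule

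*Combined protocol and SAP*

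**What the plan says.** **Sample Size Justification (B3.B).** The planning figures come from an earlier published trial and concern anxiety: "the mean (SD) of STAI anxiety score is 34(8", that is, mean 34 and SD 8. Half an SD is taken as clinically meaningful. The next paragraph names a different construct: "Our sample size calculation to detect a 4-point change in pain score". It gives 64 per group at alpha 0.05 and 80% power, raised to 76 per group for 15% loss. Subject Population gives the total of 152.

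**Data Analysis (B3.B).** The primary outcome is anxiety and pain "as measured by the VAS and VAS A scores". STAI does not appear in this section. The one planning figure for VAS is a mean: "Prostate biopsy mean VAS score with local anesthetic is around 3-4". There is no SD or target difference for VAS or VAS-A, and nothing says whether one or both must show a difference.

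**Specific Aims (B1).** Hypothesis 1.1 says SANO patients "will have decreased anxiety during the procedure, as measured by STAI (State-Trait Anxiety Inventory) score", along with S-PCS and vital signs. Hypothesis 1.2 says they "may have a decrease in pain as measured by VAS (visual analogue scale) score". VAS-A is not mentioned.

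**Instrument lists.**

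| Section | Before biopsy | After biopsy |
|---|---|---|
| Pre-procedure Evaluation (B3.A) | STAI, VAS ("the pre-procedure STAI and VAS scores will be obtained") | not covered |
| Periprocedural Data Collection (B3.A) | not covered | STAI, S-PCS |
| Privacy (B7) | VAS, VAS-A, S-PCS | VAS, VAS-A, S-PCS |

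Data Analysis also relies on VAS and VAS-A from around the procedure: "We will compare the perioperative VAS and VAS-A scores to the retrospective VAS and VAS-A scores" obtained in the survey at 2 to 10 months.

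**The concern.** A power statement means something only for the outcome, SD and difference that produced it. Here those inputs belong to STAI, the text labels the target as pain, and the analysis section makes two other scales primary. Correcting the label alone would not cure this, because the sized outcome would still differ from the declared one.

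Two things are at stake. First, power for the declared primary outcome is not established. Second, the documents do not settle which result decides the trial. STAI, VAS, VAS-A or a combination could each be defended from some section after the data are in. The missing success rule matters as much as the missing SD, because it changes both the power and the false-positive risk.

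**Working it through.** **Inputs from the documents:** STAI SD 8; threshold 0.5 SD; target 4 points; alpha 0.05; power 80%; 15% loss; 1:1 allocation; mean VAS about 3 to 4. Sidedness is not stated.

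**Reviewer assumptions:** VAS scored 0 to 10; VAS SD 1.5 to 3; correlation between VAS and VAS-A 0 to 0.9; in step 4, a true effect of 0.5 SD on each measure.

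**1. The plan's own figure.** Standardised effect d = 4/8 = 0.5.
- Normal approximation: n = 2(1.960 + 0.842)²/0.5² = 62.8, so 63 per group.
- Two-sample t-test, two-sided: n = 63.8, so **64 per group**; power at 64 is 0.801.
- The one-sided version gives 51, so the plan's figure is two-sided.
- Loss: 64/0.85 = 75.3, so **76 per group** and 2 × 76 = **152**.

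Every stated figure follows from the STAI inputs.

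**2. Could 4 points be a VAS target?**
- From a mean of 3 to 4, a 4-point fall gives 3 − 4 = −1 to 4 − 4 = 0: at or below the bottom of the scale.
- With 64 per group the detectable difference at 80% power is 0.499 SD, so 4 points implies SD = 4/0.499 = 8.0. The largest possible SD on a 0–10 scale is 5 (half the patients at each end).
- Even at SD 5, d = 4/5 = 0.8 needs only 26 per group.

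So 64 does not come from VAS.

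**3. What 64 evaluable per group offers on VAS alone** (two-sided 0.05). The 1-point target is illustrative.

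| Assumed SD | Detectable difference, 80% power | Power for 1 point | n per group for 1 point, 80% power |
|---|---|---|---|
| 1.5 | 0.75 | 96% | 37 |
| 2.0 | 1.00 | 80% | 64 |
| 2.5 | 1.25 | 61% | 100 |
| 3.0 | 1.50 | 46% | 143 |

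**4. VAS and VAS-A both primary,** 64 evaluable per group, bivariate normal approximation matched to the t-test power.
- *Both must succeed, 0.05 each.* At correlation 0: 0.801² = 0.642. At 0.5: 0.689. At 0.7: 0.715.
- *Either may succeed, 0.025 each.* Power per measure 0.712. P(at least one) = 2 × 0.712 − P(both) = 0.917, 0.852, 0.819 and 0.773 at correlation 0, 0.5, 0.7 and 0.9. Simulation with 20,000 trials each gave 0.916, 0.852, 0.822 and 0.780.
- *Fixed sequence at 0.05.* The first test keeps 0.801.
- *Either may succeed, no adjustment.* Family-wise error 1 − 0.95² = 0.0975 if independent.

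**5. Evaluable patients per group to restore 80%,** if that were wanted.
- Both must succeed: 84, 80 and 77 at correlation 0, 0.5 and 0.7. Dividing by 0.85 gives 99, 95 and 91 enrolled.
- 80% on each measure at 0.025: 78, or 92 enrolled.

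**The case against.** The strongest reply is that the number is sound whatever its label. The sample size depends only on the standardised effect, so 64 per group gives 80% power for 0.5 SD on VAS or VAS-A just as on STAI. That is correct, and it is why no shortfall is claimed. But the plan never makes that argument for VAS or VAS-A. The half-SD threshold follows directly on the STAI figures, and nothing says that it carries over to the other scales. Nor would the argument cover two primaries without a success rule.

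A second reply is that the hypotheses rank the outcomes: anxiety is expected to fall, while pain only may. This suggests that anxiety leads, but it is not a stated hierarchy, and it points to STAI whereas Data Analysis uses VAS-A. It does show that 0.5 SD on both measures may be optimistic; a smaller pain effect would lower the joint power below 64% to 71%.

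Third, the lists could mean that one anxiety scale replaced the other with incomplete editing. No section names both STAI and VAS-A. Read together, the sections plan to collect STAI, VAS and VAS-A, so it is not claimed that any of them goes uncollected. The flowchart is not visible in the text reviewed. The sponsor should confirm what is actually collected before choosing an option.

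**Conclusion.** The concern holds and must be fixed. The 64 and 76 per group are arithmetically right for a two-sided comparison of STAI with SD 8. They are mislabelled as a pain calculation and are not tied to the declared primary outcome. Power for VAS and VAS-A is not established; it is not shown to be too low.

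If both remain primary, the figure to report depends on the rule. It is about 64% to 71% if both must succeed, 71% per measure if alpha is split, or 80% for the first test in a fixed sequence. These figures assume 0.5 SD on each measure, 64 evaluable per group and correlation 0 to 0.7. That the STAI inputs give 64 needs no outside assumption beyond a two-sided test, and the mismatch with the declared primary is plain from the text.

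**What to change.** Before any comparison by group, choose one of the following. The choice is the sponsor's.

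- **(a) STAI as the single primary.** In Sample Size Justification, write: *4-point difference in STAI anxiety score (0.5 SD, SD 8)*. In Data Analysis, name post-procedure STAI as the single primary outcome and make VAS and VAS-A secondary. First confirm that post-procedure STAI is being collected.
- **(b) VAS or VAS-A as the single primary.** Replace the 4-point statement with: *64 evaluable per group gives 80% power for a 0.5-SD difference*. Add the assumed SD, its source, the detectable difference in that scale's units, and why that difference is worth detecting. Name the other scale as secondary.
- **(c) VAS and VAS-A both primary.** Give the same details for each, then the success rule with its power:
  - both at 0.05: joint power with the assumed correlation (about 64% to 71% for 0 to 0.7);
  - either at 0.025: 71% per measure and, separately, the chance of at least one success (about 92% to 82% for 0 to 0.7; 77% at 0.9);
  - fixed sequence at 0.05: the order, with 80% for the first test.

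Under every option, make Specific Aims, Pre-procedure Evaluation, Periprocedural Data Collection, Data Analysis, Privacy and, if it lists instruments, the flowchart agree on the instruments before and after biopsy. At present VAS-A is missing from the Aims and Pre-procedure Evaluation, VAS and VAS-A from Periprocedural Data Collection, and STAI from Data Analysis and Privacy. S-PCS is listed before biopsy in Privacy but not in Pre-procedure Evaluation.

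**Cost.** Wording in six sections. Enrolment of 152 can stand if 0.5 SD is accepted as the target and, under (c), any lower power is stated; holding 80% under (c) when both must succeed or alpha is split would need the larger numbers in step 5. Option (a) demotes the declared VAS and VAS-A. Options (b) and (c) need a sourced SD.

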### Data Analysis

All data will be collected and stored securely using the REDCap system. Data will be managed and analyzed by the PI and biostatistical support team at the BIDMC FIRST program. A Data Transfer Agreement will be created to allow for the study team's statistician, [name] MD/PhD at Brigham and Women's Hospital, to obtain and perform statistical analysis on de-identified data. At the conclusion of the study, de-identified study data will be exported out of REDCap and sent to [name] in a secure file via email message. Data will not be transferred until this agreement is approved and fully executed by both parties.

Primary outcome measure is patient anxiety and pain levels in the N2O group vs the oxygen only group as measured by the VAS and VAS A scores. We are specifically interested in the difference in scores between the two groups. Prostate biopsy mean VAS score with local anesthetic is around 3-4. We will also obtain a baseline pain index between the two groups. We will compare the perioperative VAS and VAS-A scores to the retrospective VAS and VAS-A scores collected during the survey administered 2-10 months after their biopsy.

We will also be obtaining 6 question Situational Pain Catastrophizing Scores for both groups and will compare the variation in response. Patients who have had a prior biopsy will also fill out a 13 question Pain catastrophizing score, which we will use as a baseline measure for biopsy related anxiety and hesitation.

Additional metric will include duration of biopsy, as measured by time in/time out of the procedure room for patients administered either nitrous or control oxygen when compared to patients who do not consent to the study (and will have no gas applied). Operator ease in performing the biopsy will be measured by 3 simple questions assessing patient positioning and ease of transrectal probe insertion. Prostate biopsies are generally performed as an outpatient procedure and patients can drive themselves home in most situations. Post biopsy side effects and ability of the patient to drive themselves home will be used as a surrogate to determine practicality of administering SANO in the outpatient setting.

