#### B4. POSSIBLE BENEFITS

It is not possible to determine whether a subjects will directly benefit from participation. Patients receiving SANO may potentially experience decreased pain and anxiety when undergoing office prostate biopsy. Benefits would not be expected to occur for those patients in the placebo oxygen arm.

Taking part in the study will increase scientific knowledge regarding the ability of the inexpensive, commonly available agent to reduce procedural pain and anxiety. Moreover, as SANO is currently being used throughout the United States for prostate biopsies, this study may help us identify risks to SANO that are currently not known or described.

If there is a significant improvement in patient anxiety and pain with the nitrous oxide, this could lead to changes in the standard of care for patients undergoing prostate biopsy.

We also may be able to identify patient factors that in the future allow us to prospectively identify patients who would be expected to experience more benefits from nitrous oxide. At the same time, this may allow us to identify patients who would not have significant benefit and might minimize their risk of exposure to nitrous oxide.

There is potential to also extend knowledge obtained in this study to other commonly performed office procedures that are associated with pain and anxiety, such as LEEPs, vasectomies, cystoscopies, and others.

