## **B7. STUDY LOCATION**

### **Privacy**

The study will be conducted on the premises of BIDMC Longwood Campus. We will obtain lists of patients intended for prostate biopsies in the following week, and study team members will review the OMR records for inclusion and exclusion criteria. The patient will be contacted by phone either from in-office phone call or through Doximity phone application (which provides the BIDMC Urology office as the caller ID). We will ask the patient whether they are in a location that affords privacy for discussion of medical information. If they are not, we will arrange an appropriate time when the patient will have privacy for study discussion. Phone interviews by study team members will be conducted in private space to avoid the interview being overheard.

Pre-procedure questionnaires will be emailed to private patient email via the REDCap server. Data collected will be kept within the REDCap server. Access to our REDCap will only be allowed for study team members who are trained in protecting PHI.

Operator Surveys will be on paper forms with patient identifying sticker on the form. At the end of the biopsy, the data will be input into the REDCap system by a study team member, and the paper version will be disposed of in a disposal unit intended for medical information waste.

Pre-procedure and post-procedure VAS, VAS-A score and Situational Pain Catastrophizing Score (S-PCS) and Trails-making Part B tests will be obtained in a private exam room where only the patient, study team members, and clinical staff measuring vitals will be present. Questionnaire answers will be input by the patient into a tablet computer. The tablet computer will be wiped with sanitizing wipe between uses given current COVID pandemic.

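### Two scales share the primary outcome with no rule for success, and the stated 80% power belongs to neither of them

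*Combined protocol and SAP*

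**What the plan says.** - **Primary outcome (B3.B, Data Analysis).** The outcome is "patient anxiety and pain levels in the N2O group vs the oxygen only group as measured by the VAS and VAS A scores", and interest is in the between-group difference in scores. The section gives no hypothesis test, success rule, testing order, alpha allocation or composite.
- **Power (B3.B, Sample Size Justification).** The section reports from a cited earlier trial that "the mean (SD) of STAI anxiety score is 34(8") and takes half an SD as clinically meaningful. It then describes the calculation as one "to detect a 4-point change in pain score (p less than 0.05 significance level"), giving 64 per group at 80% power and 76 after a 15% allowance for losses. This is the only place where an alpha appears.
- **Aims (B1, Specific Aims).** Hypothesis 1.1 says that patients given nitrous oxide "will have decreased anxiety during the procedure, as measured by STAI", the situational pain catastrophizing scale and vital signs. Hypothesis 1.2 says that they "may have a decrease in pain as measured by VAS" and vital signs.
- **Benefits (B4).** A possible change in standard of care is introduced with "If there is a significant improvement in patient anxiety and pain with the nitrous oxide".
- **Data collection.** B7 (Privacy) lists "Pre-procedure and post-procedure VAS, VAS-A score and Situational Pain Catastrophizing Score (S-PCS"). The Pre-procedure Evaluation section lists STAI and VAS. The Periprocedural Data Collection section lists post-procedure STAI and S-PCS.

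**The concern.** A single primary label covers two constructs, and the plan does not say what counts as success. A split result is plausible, because the aims are firmer about anxiety than about pain. If one scale improves and the other does not, a reader cannot tell from the plan whether the trial met its primary outcome. The rule could then be settled after the results are known, and the 0.05 in the sample-size section would not describe the conclusion drawn.

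The power statement does not resolve this. It describes one comparison, takes its SD from STAI and labels its target as pain, so it does not show which scale leads or how well either is powered. The remaining cues conflict. The contrast between will and may in the aims suggests that anxiety leads, while the benefits paragraph leans toward needing both. Neither is a decision rule.

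**Working it through.** **Inputs from the documents:** difference 4 points, STAI SD 8 (so 0.5 SD), alpha 0.05, power 80%, 15% losses, 1:1 allocation, 152 patients in total. **Assumptions:** two-sided tests (not stated, but see step 1); correlation *r* between the two scales of 0 to 0.9, with 1 as the limit; a 0.5 SD effect on each scale. The documents give no SD for VAS or VAS-A and no correlation, so the power figures in steps 3 to 5 are illustrative.

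**1. The plan's own figure.** n = 2(1.960 + 0.842)² / 0.5² = 62.8, so 63 per group by normal approximation. The t-test gives 63.8, so 64. A one-sided test gives 50, which supports the two-sided reading. For losses, 64 / 0.85 = 75.3, so 76 per group and 152 in total. The arithmetic is right for STAI.

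**2. Either scale suffices, 0.05 each.** With no true effect, the error is 1 − P(|Z₁| ≤ 1.96 and |Z₂| ≤ 1.96). At *r* = 0 this is 1 − 0.95² = 9.75%. For other values it comes from the bivariate normal distribution.

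| *r* | 0 | 0.3 | 0.5 | 0.7 | 0.9 | 1 |
|---|---|---|---|---|---|---|
| Error | 9.75% | 9.5% | 9.1% | 8.4% | 7.0% | 5% |

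These rates count rejections in both directions. A false finding in favour of nitrous oxide alone has probability 1 − 0.975² = 4.9% at *r* = 0 and 3.5% at *r* = 0.9, against 2.5% for one scale.

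**3. Both scales required, 0.05 each.** Error is held at 5% or less. With 64 per group the noncentrality is 0.5 × √(64/2) = 2.83, and power for one test is Φ(2.83 − 1.96) = 80.7% (80.1% by t-test). At *r* = 0 the power for both is 0.807² = 65%. It is 70% at *r* = 0.5 and 76% at *r* = 0.9. Simulated t-tests give 64%, 69% and 75%.

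**4. Fixed sequence, anxiety then pain.** Anxiety keeps the 80% of step 1. Pain can be claimed only if both tests are significant, so its power is the step 3 figure, 65% to 76%.

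**5. Holm across the two scales.** A given scale is claimed if its own test passes at 0.025 (|Z| > 2.241), or if it passes at 0.05 and the other passes at 0.025. Power for one test at 0.025 is 72.1%. At *r* = 0, power for a given scale is 0.721 + (0.807 − 0.721) × 0.721 = 78%. It is 77% at *r* = 0.5 and 76% at *r* = 0.9. A plain split of 0.025 each gives 72% (71% by t-test) for a given scale, so Holm is the better form of that option.

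**The case against.** The strongest reply is that the inflation depends on a rule the plan never states. Nowhere does it say that either scale is enough or that each is tested at 0.05. The primary outcome sentence and the benefits paragraph both join anxiety with pain, and if both must succeed there is no inflation. Hypotheses 1.1 and 1.2 could also be read as two separate claims, for which the need to adjust is debated.

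This stands as far as it goes. A reader might infer that the trial has a false-positive rate of 7% or more. The documents do not support that. A floor of 7.0% needs an assumed correlation of 0.9, the limit at perfect correlation is 5%, and the either-suffices rule is itself only one possible reading. A reader might also infer that the sample size is miscalculated, but it is correct for STAI. The reply does not remove the gap: requiring both scales costs power instead, and the plan chooses neither course.

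Two further points are fair. Putting anxiety first is a design preference that weakens the pain test, and that cost has to be shown. A testing rule also does not settle the test, the time point or the handling of baseline. The post-procedure lists in the Periprocedural Data Collection and Privacy sections differ on whether VAS is collected. These are separate gaps, but the rule cannot be applied until they are closed.

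**Conclusion.** The point holds as a missing decision rule together with a power statement attached to the wrong scale. What is established from the text is that two scales are primary, no section supplies a success rule, order or alpha split, and the 80% applies to a 4-point STAI difference with SD 8, not to VAS or VAS-A.

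The consequences are conditional. Under either-suffices at two-sided 0.05 each, the error is between 5% and 9.75%. Under both-required, power at 64 per group is about 65% to 76% instead of 80%, if each scale responds by 0.5 SD and the correlation is 0 to 0.9. True power on VAS and VAS-A cannot be computed from the documents. Reading VAS-A as an anxiety scale is an inference from its context.

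**What to change.** 1. **Settle the anxiety score.** Choose STAI or VAS-A as primary, and use it consistently in Data Analysis, Sample Size Justification, Specific Aims, Pre-procedure Evaluation, Periprocedural Data Collection and Privacy. State the test, time point and baseline handling for it and for VAS pain.
2. **Correct the power statement.** Replace the pain-score label and state the 80% only for STAI (4 points, SD 8). If VAS-A is kept, give its SD and restate the power.
3. **Add one rule to Data Analysis,** fixed before any comparison by arm:
   - *Sequence:* test the anxiety score at two-sided 0.05, and test VAS pain at two-sided 0.05 only if anxiety is significant. Power is 80% for anxiety (STAI) and about 65% to 76% for pain. No confirmatory pain claim is possible if anxiety fails.
   - *Holm:* apply it across the two scales at an overall two-sided 0.05. Power is about 78% to 76% for a given scale (correlation 0 to 0.9), and pain can be claimed without anxiety.

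The power figures for pain and for Holm assume 0.5 SD on both scales. The sequence follows the emphasis in the aims; Holm suits a sponsor who wants pain to stand alone.

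**Cost:** text changes only, with no added patients if STAI is the anxiety score. If VAS-A is chosen, whether 76 per group is enough is unknown until its SD is supplied. The sponsor also accepts power below 80% for pain under the sequence, or for each scale under Holm.

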###### **Baseline Assessment:**

After informed consent has been obtained, the patient will be directed to a REDCap questionnaire that will collect demographics, general medical history, and prior prostate biopsy information (See Pre-Procedure Evaluation Survey). This will be reviewed by research personnel to confirm eligibility to participate in the study based on pre-determined inclusion and exclusion criteria. If they do not qualify for the study, they will not be randomized to either arm, and will undergo a standard template biopsy with local anesthesia only.

In addition, patients will complete the Brief Pain Inventory, a well-validated measure that assesses intensity of current pain and interference of pain in the patient's life (Dworkin, 2005). If the patient

does not complete these two questionnaires electronically before the day of procedure, they will be offered the opportunity to complete on the day of their procedure prior to the biopsy.

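### The primary comparison gives the planned pre-procedure scores no role; pre-specified ANCOVA would gain precision, once the anxiety and pain instruments are reconciled

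*Combined protocol and SAP*

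**What the plan says.** Data Analysis (B3.B) makes anxiety and pain the primary outcome, "as measured by the VAS and VAS A scores", and describes the comparison in one sentence: "We are specifically interested in the difference in scores between the two groups". Neither that section nor any other names a test, model or covariate, or chooses between the post-procedure score and a change from baseline.

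Several baseline measures are planned, none with a stated part in the primary comparison:
- Data Analysis: "We will also obtain a baseline pain index between the two groups".
- Data Analysis, on the 13-question catastrophizing score for patients with a prior biopsy: "which we will use as a baseline measure for biopsy related anxiety and hesitation".
- Baseline Assessment: the Brief Pain Inventory, described as "a well-validated measure that assesses intensity of current pain".
- Day-of-biopsy scores before the procedure, as in the table.

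| Section | Before procedure | After procedure |
|---|---|---|
| Pre-procedure Evaluation (B3.A) | STAI, VAS | not covered |
| Periprocedural Data Collection (B3.A) | not covered | STAI, S-PCS |
| Privacy (B7) | VAS, VAS-A, S-PCS | VAS, VAS-A, S-PCS |

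Specific Aims (B1) measures anxiety "as measured by STAI (State-Trait Anxiety Inventory) score, situational pain catastrophizing scale (SPCS) and patient vital signs". Sample Size Justification uses a STAI mean of 34 and SD of 8, but calls the 4-point target a pain score. For VAS the only figure is "Prostate biopsy mean VAS score with local anesthetic is around 3-4"; no SD or target difference is given for VAS or VAS-A.

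**The concern.** In a randomised trial with a score taken before treatment and again after it, the pre-treatment score usually explains part of the variation in the later one. Adjusting for it narrows the confidence interval with no extra patients. In large samples ANCOVA is at least as precise as either the post-procedure score alone or the change score, whatever the correlation. This protocol plans pre-procedure scores but does not use them in the primary comparison, and it leaves the form of the analysis to be chosen later.

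The remedy cannot be written down yet, because a matching covariate needs the same instrument at both times. For anxiety the sections disagree between STAI and VAS-A. Pain has a similar gap: the procedures take VAS beforehand, but the post-procedure list omits it. Only the Privacy section has VAS and VAS-A at both times. This reading covers the text; the study flowchart (Figure 1) could not be seen.

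**Working it through.** **Inputs.** From Sample Size Justification: difference 4, SD 8 (STAI), alpha 0.05, power 80%, 64 per group, 15% allowance, 76 per group. From Subject Population: 152 in total. Sidedness is not stated. The pre/post correlation r is not in the documents and is assumed from 0 to 0.7.

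**1. The plan's own figure.** The standardised difference is 4/8 = 0.5. A two-sided two-sample t-test at 0.05 with 80% power needs 63.77, so 64 per group. Then 64/(1 − 0.15) = 75.3, so 76, and 2 × 76 = 152. A one-sided test would give 50, and 64 × 1.15 = 73.6 would give 74; neither matches. The stated size is therefore reproduced by an unadjusted two-sided comparison with a raw-score SD, and takes no credit for baseline adjustment.

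**2. Unadjusted precision at 64 per arm.** SE = 8 × √(2/64) = 1.414. With 126 degrees of freedom the 95% CI half-width is 2.80 points and power is 80.15%.

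**3. ANCOVA with one covariate.** The variance is multiplied by 1 − r², with 125 degrees of freedom. Half-width = t × 8 × √((1 − r²) × 2/64).

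| r (assumed) | 1 − r² | Power | CI half-width |
|---|---|---|---|
| 0 | 1.00 | 80.1% | 2.80 |
| 0.2 | 0.96 | 81.7% | 2.74 |
| 0.3 | 0.91 | 83.7% | 2.67 |
| 0.5 | 0.75 | 90.0% | 2.42 |
| 0.7 | 0.51 | 97.6% | 2.00 |

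At r = 0 the cost is one degree of freedom (power 0.8014 against 0.8015). At r = 0.2 the gain is 81.7 − 80.1 = 1.6 percentage points. These figures assume that every patient has a pre-procedure score.

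**4. What a change-score reading would require.** With equal SDs before and after, the variance factor is 2(1 − r). It equals 1, and so returns 64 per group, only at r = 0.5. Neither that correlation nor equal SDs is stated in the documents, whereas step 1 needs only stated inputs, apart from sidedness.

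**The case against.** The strongest reply is that an unadjusted comparison of randomised groups is valid and the stated size is correct for it, so this is a preference for efficiency. That stands, and it limits how far the point can be pressed. It is also fair that every figure above is on the STAI scale with an assumed correlation, while Data Analysis makes VAS and VAS-A primary. For pain, if the pre-procedure score predicts biopsy pain only weakly, the gain could be under 2 percentage points.

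A reader might infer that the trial is at risk of much lower power, because a change-score analysis with equal SDs would have about 51% power at r = 0 and 66% at r = 0.3. The documents do not support that inference. Words such as decrease and change appear in Sample Size Justification, so a change score is not ruled out, but the SD given is that of a raw score and Data Analysis speaks of scores differing between groups. Those lower powers belong to an analysis that the plan does not state.

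A reader might also infer that the day-of-biopsy scores are unsuitable covariates because they follow randomisation. The order is not settled. Randomisation follows the baseline assessment, which may itself be completed on the procedure day. In either case Pre-procedure Evaluation and Periprocedural Intervention place the scores in a separate room before gas starts. Privacy has patients enter their own answers, and Randomization keeps the allocation from them.

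**Conclusion.** The point holds as a precision improvement worth considering. The plan names no model for its primary comparison and gives the planned pre-procedure scores no part in it. ANCOVA on the matching score would raise power from 80% to between 80% and 98%, and reduce the CI half-width from 2.80 to as little as 2.00 points, for assumed correlations from 0 to 0.7. These results rest on the STAI inputs and 64 evaluable patients per arm. They carry over to VAS or VAS-A only if the target is again 0.5 SD. They do not show that 76 per group is adequate for those scales.

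**What to change.** 1. Reconcile Specific Aims, Pre-procedure Evaluation, Periprocedural Data Collection, Sample Size Justification, Data Analysis and Privacy, so that the same anxiety scale and the same pain VAS are collected both before gas starts and after the procedure.
2. Pre-specify in Data Analysis that each post-procedure primary score is compared between randomised arms by ANCOVA with the same instrument's pre-procedure score as covariate, reporting the adjusted mean difference and its 95% confidence interval.
3. Fix this before anyone on the study team, or the statistician, looks at outcome data by arm. The point at which "de-identified study data will be exported out of REDCap" is too late: it comes at the end of the study, the site team also manages and analyses the data, and blinding is described for patients only.
4. Keep patients with a missing pre-procedure score in the analysis, for example by simple baseline imputation that ignores arm. A complete-case ANCOVA would drop them and give back some of the gain.

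The cost is wording in up to six sections and, if the chosen anxiety or pain score is now collected at only one time point, one short self-report score at the other. ANCOVA needs no more patients than the unadjusted analysis. If VAS and VAS-A remain primary, Sample Size Justification also needs an SD and a target difference for them, whichever model is used.
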